4.2 Secondary Outcomes

- Patient compliance survey: Patients will be assessed for compliance on the morning of surgery.
- Visual assessment of wound healing and scar formation will be performed at each post-operative visit.
- Patients will be asked about any side effects regardless of intervention arm- the percentage of patients who report side effects, including rashes, irritation, or allergic reactions will be calculated for each intervention.

5. Populations to be Analyzed

Inclusion Criteria: deemed healthy enough for orthopedic surgery, age 18 and older, willing to comply with study protocol, and without clinical signs of skin infection.

Exclusion Criteria: previous allergic reaction or absolute contraindication to topical chlorhexidine gluconate or any other study product ingredient, dermatologic disorders around the surgical site, signs of other infections, age under 18, pregnancy.

Patients will be randomly placed into study cohort.

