- 4. Patient Reported Outcome Scores (PROMIS): PROMIS scores are clinical outcome questionnaire taken on iPad with emerging questions that change based on participant’s response. <http://www.healthmeasures.net/explore-measurement-systems/promis>**
- 5. Foot Function Index (FFI) questionnaire (attached)**
- 6. Visual assessment of wound healing and scar formation will be performed at each post-operative**

visit

7. Patients will be asked about any side effects regardless of intervention arm- the percentage of patients who report side effects, including rashes, irritation, or allergic reactions will be calculated for each intervention.

15. Background - in nontechnical, lay language

Summarize in 2-3 paragraphs past experimental and/or clinical findings leading to the design of this protocol. Include any relevant past or current research by the PI. For drug and device studies, summarize the previous results (i.e., Phase I/II or III studies).

FOR 200 Revised 4/23/2020 Page 9 of 16 07/29/19

There is currently no clear consensus in the surgical community regarding the best local surgical site treatment protocol for the prevention of surgical site infections. The most recent CDC guidelines on antiseptic prophylaxis from 2017 recommend the following:

“8A.1 Advise patients to shower or bathe (full body) with soap (antimicrobial or nonantimicrobial) or an antiseptic agent on at least the night before the operative day. (Category IB—strong recommendation; accepted practice.)

8A.2 Randomized controlled trial evidence suggested uncertain trade-offs between the benefits and harms regarding the optimal timing of the preoperative shower or bath, the total number of soap or antiseptic agent applications, or the use of chlorhexidine gluconate washcloths for the prevention of SSI. (No recommendation/ unresolved issue.)” [1]

Without a clear consensus on the best standard of care in this area and with uncertainty surrounding the efficacy and limitations of chlorhexidine gluconate (CHG), there is a need for more research in this area. This study hopes to compare a commercially available presurgical bath wipe, Theraworx™, to 2% chlorhexidine gluconate and simple bathing in adult patients undergoing orthopedic surgery.

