- g. Will participants incur any costs as a result of their participation? Yes No **If Yes, describe the reason for and amount of each foreseeable cost.**
- h. Will participants be compensated? Yes No **If Yes, complete i-v.**
- i. Type: (e.g., cash, check, gift card, merchandise):
- ii. Amount or Value:
- iii. Method (e.g., mail, at visit):
- iv. Timing of Payments: (e.g., every visit, each month):
- v. Maximum Amount of Compensation per Participant:

18. Benefits

Describe the potential benefits of the research. **The research has the potential to benefit the U.S. health care system, surgeons, and patients. In recent years, surgical site infections occur in about 2% of all patients undergoing orthopedic procedures. Surgical site infections often necessitate longer hospital stays, increased use of antibiotics, and even revision surgery and puts economic burden on patients, physicians, and hospitals. This research aims to highlight the effectiveness of Theraworx™ wipes to reduce the rate of surgical site infections and to introduce the wipes as a part of the standard skin preparation for various orthopedic procedures.**

19. Risks - in nontechnical, lay language

- a. List the known risks for participants as a result of participation in the research. This should not include the minimal risk of loss of confidentiality. However, it should include any physical, psychological, social, economic, and/or legal risks. If there is a greater than minimal risk of loss of confidentiality describe why this is so. Do not list risks associated with the standard-of-care procedures.

FOR 200 Revised 4/23/2020 Page 13 of 16 07/29/19

NOTE: Risks included here should be included in the consent form or information sheet, as applicable. The major risk of this study is possible allergic or serious skin reaction to the 2% topical Chlorhexidine Gluconate or Theraworx™ wipes. Up to 10% may experience dryness, itching, or rash on the application site. Very rarely (less than 1% of patients), patients may experience a serious allergic reaction within minutes after the application of the wipe.

- b. Estimate the frequency, severity, and reversibility of each risk listed. N/A
- c. Is this a therapeutic study or intervention? Yes No **If Yes, complete i.-iii.**
- Describe the standard of care in the setting where the research will be conducted:
 - Describe any other alternative treatments or interventions:

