 - Describe any withholding of, delay in, or washout period for standard of care or alternative treatment that participants may be currently using:
- d. Do you foresee that participants might need additional medical or psychological resources as a result of the research procedures/interventions? Yes No **If Yes**, describe the provisions that have been made to make these resources available.
- e. Do the benefits or knowledge to be gained outweigh the risks to participants? Yes No **If No**, provide justification for performing the research:

20. Precautions/Minimization of Risks

- a. Describe precautions that will be taken to avoid risks and the means for monitoring to detect risks. **There are minimal risks and risk of randomization involved with this study. Even so, patients will be in the clinic under the care of the nursing staff and the operating team. Patients will be closely monitored for any adverse reaction due to the topical products before their surgery begins. Patients will also be informed about the possibility of adverse reactions and instructed to discontinue use and seek immediate medical attention if they experience any signs or symptoms of serious adverse effects or severe allergic reactions. Patients with contraindications to any of the interventions will be excluded from the study.**

If the protocol involves drugs or devices skip Items 20.b. and 20.c. and go to Item 21. Instead, include this information in the [Drug Review Sheet](#) or [Device Review Sheet](#), as applicable.

- b. If hazards occur to an individual participant, describe (i) the criteria that will be used to decide whether that participant should be removed from the protocol; (ii) the procedure for removing such participants when

necessary to protect their rights and welfare; and (iii) any special procedures, precautions, or follow-up that will be used to ensure the safety of other currently enrolled participants.

- c. If hazards occur that might make the risks of participation outweigh the benefits for all participants, describe (i) the criteria that will be used to stop or end the entire protocol and (ii) any special procedures, precautions, or follow-up that will be used to ensure the safety of currently enrolled participants. N/A

21. Informed Consent

- a. Do you plan to obtain informed consent for this protocol? Yes No **If Yes**, complete the items below.

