5.1 Populations

Control group: 160 patients who will receive only standard skin preparation prior to surgery.

Intervention group 1: 160 patients who will be administered 2% Chlorhexidine Gluconate wipes once on the night prior to surgery and once on the day of surgery in addition to standard skin preparation.

Intervention group 2: 180 patents who will be administered Theraworx™ wipes once on the night prior to surgery and once on the day of surgery in addition to standard skin preparation.

Intention-to-Treat

All randomized study subjects. This will be the primary population for analysis.

Per Protocol

All randomized study subjects completing the whole study period (complete cases). For a specific analysis, study subjects with missing data on any of the variables in the model will be excluded from the analysis.

6. Analyses

The primary analysis will compare intervention groups and their respected rate of infection between baseline, 2-weeks, 6-weeks, and 3 months using a linear mixed model. Difference in infection rate from baseline to time points where it is measured during the study will be the dependent variable. Study subjects will be considered as random effects, treatment group and visit number as fixed effects.

Patient compliance was monitored via patient questionnaires on the date of surgery. If compliance rate differed significantly, it would be labeled as a confounding factor.

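### The side-effect outcome pools local skin reactions with allergic reactions in one percentage, and no comparison with control is planned although every arm is asked

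*SAP*

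**What the plan says.** SAP 4.2 lists side effects as a secondary outcome. Who is asked: "Patients will be asked about any side effects regardless of intervention arm". What is reported: "the percentage of patients who report side effects, including rashes, irritation, or allergic reactions will be calculated for each intervention". Outcome 7 in protocol 14.b has the same wording. Neither place gives a severity grade, a category for serious reactions or a time of assessment.

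Protocol 19.a treats the reactions as two different risks. On local reactions: "Up to 10% may experience dryness, itching, or rash on the application site". On allergy: "Very rarely (less than 1% of patients), patients may experience a serious allergic reaction within minutes after the application of the wipe".

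SAP 5.1 names its arms a control group of 160, intervention group 1 of 160 (chlorhexidine wipes) and intervention group 2 of 180 (Theraworx wipes). SAP section 4 refers the reader to section 6 for the analyses. Section 6 contains a model for infection and a remark on compliance, and nothing on side effects.

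Protocol 20.a adds a safeguard outside the outcome: "Patients will be closely monitored for any adverse reaction due to the topical products before their surgery begins". No text links that monitoring to an outcome or an analysis.

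**The concern.** The protocol separates a common local reaction from a rare serious one, and the outcome then adds them together. A sum dominated by the common part says little about the rare part, which is what a surgeon would most want to know before adding a wipe to routine preparation. Protocol item 18 puts surgical site infection at about 2% of orthopaedic procedures. On that general figure the absolute benefit could not exceed about 2 points, so even a small excess of serious reactions would matter to the balance.

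The second part is the missing contrast. Every arm receives standard skin preparation and surgery, and both may cause skin complaints. A wipe-arm percentage on its own therefore does not isolate what the wipe adds. The SAP's phrase about each intervention also leaves open whether a control percentage will be reported at all, because the SAP uses the word intervention for the two wipe arms only.

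**Working it through.** The documents give no sample-size, power or control-rate figure for side effects, so there is no stated result to reproduce. The arm sizes do add up: 160 + 160 + 180 = 500.

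**Inputs.** Arm sizes 160 and 180 (SAP 5.1). Local reaction up to 10% and serious allergic reaction under 1% (protocol 19.a). Both rates are ceilings, not expected values.

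**1. Make-up of the percentage** (count = n × p)
- Local reactions: 160 × 0.10 = 16; 180 × 0.10 = 18.
- Serious reactions: 160 × 0.01 = 1.6; 180 × 0.01 = 1.8, as upper limits.
- Local share, if no patient has both: 10 / (10 + 1) = 91%.
- The share depends on both rates. With 10% local and 0.5% serious it is 10 / 10.5 = 95%. With 5% local and 1% serious it is 5 / 6 = 83%.

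**2. Whether a difference in serious reactions would show**
- Two serious reactions against none moves the percentage by 2/160 = 1.3 points or 2/180 = 1.1 points.
- The 95% half-width for a difference between two arms at 10% each is 1.96 × √[0.09 × (1/n₁ + 1/n₂)].
- Wipe against wipe (160 and 180): 6.4 points. Two arms of 160: 6.6 points.
- The shift is about one-fifth of the half-width or less (1.3 / 6.4 = 0.20).

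**3. What separate reporting of serious reactions would give**
- Chance of at least one event at the 1% ceiling, 1 − 0.99ⁿ: 80% (n = 160) and 84% (n = 180).
- One-sided 95% upper bound if none occur, 1 − 0.05^(1/n): 1.9% (n = 160), 1.7% (n = 180), 0.9% (both wipe arms, n = 340).
- Power of Fisher's exact test for 1% against 0%, two-sided 5%: about 1% or less for either wipe against control.
- About 1,059 per arm would be needed for 1% against 0.1% at 80% power (normal approximation).
- Separate reporting therefore gives a visible count and a bound, not a usable comparison.

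**4. What a control contrast would give for the common reactions**

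The documents give no control rate, so I assume a range. The comparison is 10% in a wipe arm against control, 160 per arm, two-sided 5%.

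| Assumed control rate | Power, normal approximation | Power, Fisher |
|---|---|---|
| 1% | 95% | 95% |
| 2% | 86% | 83% |
| 3% | 72% | 66% |
| 5% | 40% | 32% |

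At an assumed control rate of 3% or 6%, the 95% half-width for the difference is 1.96 × √[(0.09 + 0.0291)/160] = 5.3 points or 1.96 × √[(0.09 + 0.0564)/160] = 5.9 points. The contrast is informative if the control rate is low, and less so as it rises.

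**The case against.** The strongest reply is that the plan already collects what is needed. Patients are asked whatever their arm, so a control percentage can be set beside each wipe percentage. The list of reactions reads as examples and does not rule out a breakdown by type. No between-arm effect analysis is planned for the other secondary outcomes either, so this is one case of a wider gap. The protocol form also directs hazard information to drug or device review sheets if those apply. Those sheets and any side-effect questionnaire are not in the file, so grading may exist there.

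Much of this stands, and it rules out three stronger readings that a reader might infer.

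- **That the outcome cannot show any excess over standard preparation.** Control reports appear to be collected. The contrast is unplanned and the wording ambiguous; the comparison is not impossible. Nor does any text attribute the raw wipe-arm percentage to the wipe. Any figure for the share due to standard preparation would rest on an assumed control rate.
- **That pooling is what prevents a comparison of serious risk.** Pooling hides the events, but the arm sizes are the main limit. The word serious also comes from protocol 19.a; the SAP speaks only of allergic reactions.
- **That reactions seen by staff should be added to the counts.** The monitoring in protocol 20.a is aimed at reactions to the topical products. Only the surgeons are stated to be unaware of assignment, while a research nurse or fellow consults the allocation list (protocol 17.a; SAP section 2). Merging such observations could raise the wipe-arm counts and inflate the difference from control.

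What the reply does not answer is that the measure, as written, drops a distinction the protocol itself makes, and that section 6 leaves a nearly free comparison out.

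**Conclusion.** The point holds as a weakness in how the outcome is specified. At the protocol's ceilings about 91% of the pooled percentage would be local reactions, and two serious reactions against none would move it by 1.1 to 1.3 points against a half-width of about 6.4. A difference in serious reactions would not be seen in it. The wipe-versus-control difference for the common reactions is available from data the plan appears to collect, but is not planned.

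This rests on the protocol's ceilings rather than expected rates, no overlap between the two kinds of reaction, full arm sizes, normal-approximation intervals and a two-sided 5% level. The power figures also rest on assumed control rates of 1% to 5%. The primary outcome is not affected.

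**What to change.** In SAP 4.2, replace the single percentage with two patient-reported measures for all three arms, naming control explicitly:

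1. Serious allergic reaction: number of patients and denominator in each arm, with an exact confidence interval. The investigators should state what counts as serious, since protocol 19.a uses the term without defining it.
2. Local skin reaction (dryness, itching, rash, irritation): number and percentage in each arm.

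In SAP section 6, add the risk difference for local skin reaction, each wipe minus control, with a 95% confidence interval. Plan no comparative test for serious reactions.

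If reactions seen during the 20.a monitoring are recorded, list them in a separate table by arm and keep them out of the between-arm comparison.

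The cost is SAP wording and one extra table. Two limits should be stated. The serious-reaction row is descriptive only: fewer than 2 expected events per wipe arm, and an upper bound near 1.7% to 1.9% if none occur. The split also needs answers that record the type of reaction; if the form held only a yes or no, the SAP should say so and report the pooled percentage by arm with its difference from control.

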5.1 Populations

Control group: 160 patients who will receive only standard skin preparation prior to surgery.

Intervention group 1: 160 patients who will be administered 2% Chlorhexidine Gluconate wipes once on the night prior to surgery and once on the day of surgery in addition to standard skin preparation.

Intervention group 2: 180 patents who will be administered Theraworx™ wipes once on the night prior to surgery and once on the day of surgery in addition to standard skin preparation.

Intention-to-Treat

All randomized study subjects. This will be the primary population for analysis.

Per Protocol

All randomized study subjects completing the whole study period (complete cases). For a specific analysis, study subjects with missing data on any of the variables in the model will be excluded from the analysis.

6. Analyses

The primary analysis will compare intervention groups and their respected rate of infection between baseline, 2-weeks, 6-weeks, and 3 months using a linear mixed model. Difference in infection rate from baseline to time points where it is measured during the study will be the dependent variable. Study subjects will be considered as random effects, treatment group and visit number as fixed effects.

Patient compliance was monitored via patient questionnaires on the date of surgery. If compliance rate differed significantly, it would be labeled as a confounding factor.

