- Include the [HIPAA Authorization](#) form, complete except for participant name and IRB protocol number, as the final page of the consent form

- PI requests waiver of authorization to use the information

- Attach [Waiver of Authorization and Informed Consent](#) form

NOTE: For BVAMC research, the BVAMC HIPAA authorization form or UAB HIPAA waiver form must be completed and submitted with the HSP.

PROPOSED RESEARCH

- The IRB will not accept grant applications and/or sponsor's protocols in lieu of the items as outlined below.
- Do not separate responses from items. Instead, insert your response to each item below the item, keeping the information in the order of this form.

14. Purpose - in nontechnical, lay language

a. Summarize the purpose and objectives of this protocol in one short paragraph.

The purpose of this protocol is to assess the effect of the addition of 2 doses of 2% topical chlorhexidine gluconate wipes or topical Theraworx™ wipes to standard ChloroPrep skin preparation on patients undergoing orthopedic surgery procedures. Our objective is to test the hypothesis that administration of 2% topical chlorhexidine gluconate or topical Theraworx™ wipes (one dose the night before surgery and one on the day of surgery) will reduce the number of surgical site infections in patients undergoing orthopedic surgery procedures. Furthermore, we will explore whether the rate of surgical site infections from patients who utilized 2% topical chlorhexidine gluconate wipes significantly differs from those who utilized topical Theraworx™ wipes. We hope to reduce the rate of surgical site infections with this intervention.

b. Describe how outcomes will be measured for this protocol.

Primary Outcome:

1. Clinical evaluation for presence of SSI (and standard of care culture etiology, if SSI is present) at all follow-up visits.

Secondary Outcomes:

- 1. Patient compliance survey: Patients will be assessed for compliance on the morning of surgery.**
- 2. Patient satisfaction: Patient satisfaction will be measured by asking each subject a single subjective question at baseline and each subsequent follow-up visit. Subjects will be asked “How satisfied are you with your orthopedic care?” Response options include: “Very Satisfied, Satisfied, Dissatisfied, and Very Dissatisfied”.**
- 3. Patient Pain scores: Patients will be asked to rate their pain on a 1-10 scale at each visit.**

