4.1 Primary Outcome

Infection rate between the three study cohorts. Signs and symptoms of infection will be measured at the 2-week, 6-week, and 3-month visits.

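### The primary linear mixed model, as written, estimates an arm difference averaged over visits, not the difference in the proportion of patients with an SSI

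*SAP*

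**What the plan says.** SAP Section 4.1 gives the primary outcome as "Infection rate between the three study cohorts" and adds that "Signs and symptoms of infection will be measured at the 2-week, 6-week, and 3-month visits". Protocol item 14.b words it as "Clinical evaluation for presence of SSI (and standard of care culture etiology, if SSI is present) at all follow-up visits". The objective in the SAP Introduction and in Protocol item 14.a is to lower the number of SSIs.

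SAP Section 6 compares the arms on "rate of infection between baseline, 2-weeks, 6-weeks, and 3 months using a linear mixed model". It then states: "Difference in infection rate from baseline to time points where it is measured during the study will be the dependent variable". The model terms follow: "Study subjects will be considered as random effects, treatment group and visit number as fixed effects".

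The primary population, in SAP Section 5.1, is "All randomized study subjects. This will be the primary population for analysis".

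Section 6 has no group-by-visit interaction, no named primary contrast and no per-patient endpoint. It does not say whether a patient with an SSI at one visit is still scored as infected at the next. No other primary analysis is given. SAP Section 2 separately mentions a comparison of infection rates after one year of follow-up.

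**The concern.** A patient has one index operation and either does or does not develop an SSI. The natural reading of the outcome and the objective is the proportion of patients infected in each arm. A model with several rows per patient, and with group and visit as the only fixed effects, targets something else: the mean over visits of the per-visit arm difference. That mixes how many patients were infected with how long infections lasted or when they were found.

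The group coefficient would be reported as the difference in infection rate. Two analysts who follow the SAP faithfully, one scoring an SSI only while present and one carrying it forward, could report different primary estimates from the same patients. At the 2% background rate in Protocol item 18, about 10 infections are expected in 500 patients (500 x 0.02), so each infection's weight matters.

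**Working it through.** The plan states no figure for this point, so there is none to reproduce.

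**Inputs from the documents.** Arms of 160 (control), 160 (CHG) and 180 (Theraworx), SAP Section 5.1. Three post-operative visits, SAP Section 4.1. SSI rate about 2%, Protocol item 18. Model terms, SAP Section 6. Eligible patients have no clinical infection at entry, so baseline is 0 and change from baseline equals the visit value.

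**Assumptions.** Complete visits, two-sided 0.05, and the durations and onset times stated below.

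**1. What the group term is.** With a random subject intercept, complete visits and no interaction:

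group coefficient = (d2w + d6w + d3m) / 3, where d is the arm difference at each visit.

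Equivalently, it is the arm difference in each patient's mean k/3, where k is the number of visits scored positive. Under present-at-visit coding, k is the number of visits at which the SSI is present. Under ever-infected coding, k = 3, 2 or 1 for an SSI found at 2 weeks, 6 weeks or 3 months. The coefficient equals the difference in patients infected only if k = 3 for every SSI. If baseline were kept as a fourth row with value 0, the divisor would be 4.

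**2. Same pattern in both arms.** Illustrative proportions ever infected of 3.0% and 1.5%, true difference -1.5 points. Fitted mixed models agree with the algebra:

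| Pattern | Weight | Estimate (points) |
|---|---|---|
| Present at one visit only | 1/3 | -0.5 |
| Present at two visits | 2/3 | -1.0 |
| Ever-infected, onset in equal thirds | (3+2+1)/9 = 2/3 | -1.0 |
| Ever-infected, all found at 3 months | 1/3 | -0.5 |
| Ever-infected, all found by 2 weeks | 1 | -1.5 |

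For 8/160 against 4/160 with ever-infected coding and onset 50/25/25, the weight is 0.50 x 1 + 0.25 x 2/3 + 0.25 x 1/3 = 0.75. The true difference is 2.5% - 5.0% = -2.5 points, and the estimate is 0.75 x (-2.5) = -1.9 points.

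**3. Different patterns, nearly equal risk.** Take 3/160, 3/160 and 4/180. The true differences from control are 0 and 2.22% - 1.88% = +0.35 points. Let control SSIs be present at three visits and wipe-arm SSIs at one:

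- Control mean: 3 x 1/160 = 1.875%. CHG: 3 x (1/3)/160 = 0.625%. Theraworx: 4 x (1/3)/180 = 0.741%.
- Estimates: -1.25 and -1.13 points.
- Pooled within-arm sum of squares: 2.944 + 0.327 + 0.435 = 3.705; divided by 497 this is 0.00746. The SE for CHG is sqrt(0.00746 x 2/160) = 0.0097, so p = 0.20. For Theraworx p = 0.23.

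With two visits against one, the estimates are -0.6 and -0.5 points (p = 0.39 and 0.47).

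**4. Error rate of the written model.** By exact enumeration, all arms at 2% and infections present at all visits, the rejection rate for CHG against control is 4.9%.

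**5. Variance pooled over three arms (secondary).** Under the same setting, but with one wipe inert at 2% and the other effective, an inert CHG differs from control 7.4% of the time if Theraworx lowers the rate to 1%, and 12.6% if it lowers it to 0%. About half of these rejections favour CHG (3.7 and 6.3 percentage points).

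**6. Patient-level comparison.** An uncorrected chi-square on one value per patient has size 4.5% (160 v 160) and 4.6% (160 v 180) at 2%. Its power for 2% against 1% is 9.8% and 10.3%. At 2/1/1% the SAP model rejects 12.7% and 13.2% of the time.

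**The case against.** **The null-case shift is contrived.** It needs long infections in one arm and short ones in the others with equal incidence, and the documents give no durations or onset times. That stands, and even then the shift is not significant at about 2%. The attenuation in step 2, however, needs no difference in pattern between arms.

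**The model does not invent effects when the wipes do nothing.** This also stands. A reader might infer that averaging over visits will produce spurious wins for the wipes. The documents do not support that: if neither wipe works, duration and onset have the same distribution in every arm and the test keeps close to its level (step 4). The excess in step 5 arises only when one wipe works and the other does not, and comes from pooled variance rather than visit averaging.

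**The target is inferred.** The documents speak of an infection rate and a number of infections, and nowhere define the proportion of patients infected by 3 months. This stands in part. With one operation per patient, that proportion is the natural reading, but the SAP must say so and must settle the one-year comparison.

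**An interaction may be intended.** Section 6 lists several time points, so a reader might infer visit-specific contrasts. The model sentence names only group and visit, and no contrast is chosen. An interaction read at 3 months would recover the proportion infected only with ever-infected coding, which is not stated either. With present-at-visit coding it gives 3-month prevalence.

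**Conclusion.** The concern holds and needs to be fixed before the primary result is reported. As written, the only primary analysis estimates a visit-averaged difference. It matches the difference in patients infected only under a condition that the SAP does not state: every SSI present by 2 weeks and counted at all later visits. Under the assumed patterns, a true difference shrinks to between one third and three quarters of its size when arms share a pattern. In the extreme case of differing patterns, nearly equal risks appear as a reduction of about 1.1 to 1.25 points.

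The conclusion about the target rests on the model terms and on complete visits. The sizes rest on the assumed durations and onset times. The finding concerns what is estimated and how large it looks. It does not show that the trial would wrongly declare a wipe effective when neither works. The pooled variance is a real but secondary weakness.

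**What to change.** Replace the first paragraph of SAP Section 6 with:

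> Primary endpoint: any SSI from surgery through the 3-month visit (yes/no), one value per patient, in all randomised patients. Each wipe is compared with control on this patient-level proportion, using a two-arm test suited to few events, with the risk difference and a 95% CI.

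Then:

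- Name the test in advance. An uncorrected chi-square has size of about 4.5 to 4.6% at 2%; exact tests are more conservative. The choice is the sponsor's.
- Keep CHG against Theraworx exploratory.
- Delete the sentence that makes change from baseline the dependent variable.
- Reconcile the 3-month analysis with the one-year comparison in SAP Section 2 and state which is primary.
- If outcome data have already been seen, disclose in the SAP and the report that the primary analysis was changed afterwards. The SAP is dated 2/6/22 and describes compliance monitoring in the past tense, so this is possible.

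**Cost.** A SAP amendment that uses data already planned. Some apparent power is lost: at 2/1/1%, about 10% per wipe for the unadjusted chi-square against 12.7% and 13.2% for the SAP model. The change does not cure the low power of 500 patients at this event rate.
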